9. CONSENT PROCESS

Informed consent will be administered by approved individuals trained in human subjects regulations and informed consent procedures, with appropriate VAMC and University training certifications on file and up to date. These individuals will first be asked to read the treatment protocol, and will then attend a training for study personnel given by the PI and other team members on how to provide information about the study and obtain consent for participation in the study (i.e., informed consent), and will role play until the PI determines excellent competency in this area. This is so that each person collecting informed consent is familiar with all study aspects.

All patients will complete intake assessment with study staff. As reported in the inclusion/exclusion criteria, those patients who report clinical symptoms that suggest therapy for PTSD is not in their best interest at this time will be excluded from the study and alternate care provided as appropriate. Patients who appear to meet criteria for entry into the study will be informed of the study and if interested will review consent with study personnel (PI, study coordinator, or study evaluator). During review of consent, study staff will detail study procedures and ensure that patients understand. Study staff will ensure that potential participants understand the study and are interested and able to complete study procedures prior to signing consent. Patients will receive emergency contact information for use in case of acute exacerbation of symptoms in the consent document. Patients will be informed that they can withdraw from the study at any time and receive alternate care outside of the study in outpatient psychiatry. Patients who report imminent suicidality or intolerance for study procedures at any point during the protocol may be withdrawn from the study and receive alternate care as appropriate (i.e., inpatient hospitalization, treatment in outpatient psychiatry, etc.). Consent will be written, signed, and documented in CPRS.

Timing and Location of Informed Consent. After communicating with the PCMH provider, potential Veterans will meet with a member of the research team and have the study explained to them in a safe and private location with the opportunity to ask any questions. Informed consent will be collected in research offices where potential candidates will be invited to learn about the study and that they will have a 50-50 chance, like a coin toss, to be assigned to either condition. Informed consent will be collected in a private, interruption free environment. Potential candidates will not be required to make a decision to participate at this initial contact, though that possibility will be available. If they wish to discuss participation with significant others, they will be encouraged to do so. If any potential volunteers are illiterate, the consent form will be verbally read and explained in the presence of a witness.

To reduce the burden of participating in research we may use VA approved teleconsent methods.

After discussing teleconsent procedures during screening, study staff will mail a paper consent form to the patient along with a self-addressed, stamped envelope and instructions on how to access the videoconference platform. At the scheduled day and time of consent, staff will contact patients via videoconference from a VA device (computer, laptop, tablet or phone) and begin the teleconsent session. During the teleconsent video session, project staff will explain the purpose of the research, the nature of the intervention, potential benefits and risks, the voluntary nature of participation, and the data collection procedures. The study staff and the consent form will make it clear that the individual's eligibility for services will not be affected by the decision to participate in the study. They will be informed that they are being asked to participate in a research study. They will be told the nature of the procedures, informed of risks associated with their participation, asked to read the consent form, and encouraged to ask questions or discuss any pertinent issues. If patients agree to consent, they will be asked to sign applicable areas of the consent/HIPAA form. Research staff will ask patients to hold up the signed forms to the camera so that the consenter may take a screen shot of the signature. These

images will be stored on the secure VA research network. Participants will then be asked to mail back the completed, signed consent form in the return envelope provided.

Per VA Directive 6609 instructions for mailing sensitive materials, study staff will attach a notice with the following language on the front of any mailed consent paperwork, and instruct participants to attach it to the completed paperwork to be returned:

NOTICE!!!

1. Access to these records is limited to: AUTHORIZED PERSONS ONLY.
2. Information may not be disclosed from this file unless permitted by all applicable legal authorities, which may include the Privacy Act; 38 U.S.C. §§ 5701, 5705, 7332; the Health Insurance Portability and Accountability Act; and regulations implementing those provisions, at 38 C.F.R. §§ 1.460 – 1.599 and 45 C.F.R. Parts 160 and 164.
3. Anyone who discloses information in violation of the above provisions may subject to civil and criminal penalties.

To mitigate risk, study staff will instruct the participant to only sign those areas of the consent/HIPAA that must be in the participant's handwriting. Other areas of the forms (such as the name of the participant and date at the top of each page of the consent) will be completed by study staff once the paperwork is returned. Note that study staff expects this form of consent to be rare, and will only be offered to participants with unavoidable barriers that prevent them or study staff from consenting in person. Absolutely no study procedures will begin until study staff completes the consent process.

Randomization Procedures. A randomized block randomization schedule will be generated. Participants will be randomly assigned (1:1) to one of the two study conditions. After determining eligibility, enrolled patients will be randomized to treatment groups using a web-based computer generated randomization scheme. The randomization results then will be recorded on the master tracking table. Randomization will occur at the patient level. Once a patient is randomized and attends the first session, he or she will be entered into the study and included in the intent-to-treat analysis plan. The only members of the research team who will be aware of randomization assignment will be the project therapists, the research assistant and coordinator, and the statistical analyst in charge of randomization.

Compensation for Participation. All participants will receive \$50 for the baseline assessment. After randomization, participants will receive \$50 for the 6 week assessment, \$50 for the 12 week assessment, and \$50 for the 24 week assessment for a combined total of \$200. The VA will either directly deposit the compensation into the participant's bank account, or if they do not have a bank account, participants can pick up their check from the agent cashier inside the Ralph H. Johnson VAMC. It can take up to 60 days to receive compensation.

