3. STUDY DESIGN

We will conduct a RCT to evaluate improvement in function with PE-PC compared to PCMHI-TAU among Veterans with PTSD symptoms in PC (see Figure 2 for RCT study flow). Veterans presenting in PC with chronic PTSD symptoms of at least 3 months duration who meet minimal inclusion/exclusion criteria will be randomly assigned to PE-PC (four to six, 30-minute in person or telehealth sessions) or PCMHI-TAU over 4-6 weeks. TAU will include the current standard of PTSD care in PCMHI (medication, referral to specialty MH, etc.). The type of TAU used will reflect the current practice in PCMHI and will not be constrained in the study design. All care received will be closely monitored and recorded. All Veterans will complete a baseline assessment (week 0) prior to randomization and follow-up assessments at weeks 6 (post), 12, and 24 post-baseline. Primary outcome will be the total score of World Health Organization Disability Assessment Schedule (WHODAS). Secondary outcomes will be Brief Inventory of Psychosocial Function (B- IPF), Clinician Administered PTSD Scale-5 (CAPS5) and Patient Health Questionnaire-9 (PHQ-9). If WHODAS shows floor or ceiling effect, the overall impairment score of the B-IPF will be used as a primary outcome measure.

To achieve these objectives, the study will have two phases. Phase one will include regulatory start-up and review, as well as study team training for coordinators, PCMHI providers, evaluators, and the rest of the PCMHI team. [name] and [name] have an established training protocol and will augment with

training case recording ratings to establish competence prior to the therapist seeing randomized study patients. This process will be facilitated since the recruiting site already has many of the staff as providers. Phase two will be an RCT of functional outcomes for PE-PC compared to PCMH-TAU in PC patients with PTSD. Veterans who present in VHA PC with PTSD symptoms who meet minimal inclusion criteria will be randomly assigned to receive PE-PC or PCMH-TAU. Primary outcome will be function of WHODAS) assessed at baseline, week 6, week 12, and week 24. Utilization of MH and overall VHA services will also be examined. Secondary outcomes will include PTSD severity (CAPS5) and depressive symptoms. RCT outcomes will be examined using linear modeling.

FIGURE 2. Study Design

Treatment Conditions.

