study, with minor modifications that will occur in our first 3 months of the study for use in VHA. Treatment content was drawn from the PE model. PE components include: imaginal exposure, in vivo exposure, psychoeducation, and processing. These four components are all included in PE-PC at a lower “dose” based on repetition or duration of session. Breathing was not included based on dismantling research showing no benefit and possible interference with outcome in other anxiety disorder, such as panic disorder. At the first 30-minute appointment, the PCMHI provider will review the “Confronting Uncomfortable Memories” activity workbook to be completed at home and brought back for use in subsequent appointments. The workbook asks the Veteran to write a detailed first-person narrative of the event associated with the greatest level of current distress, including recollection of personal thoughts, feelings, and physical reactions. Emotional processing questions are also included. In addition, the PCMHI provider will plan for in-vivo exposure activities between appointments. The Veteran will be instructed to complete the memory exposure for 30 minutes each day between appointments. At the second 30-minute appointment, the PCMHI provider will review the Veteran’s exposures, problem-solve any implementation difficulties, and process the exercises. The Veteran will then read the narrative and his or her answers to the emotional processing questions out loud and they will process the exercise. Practice continues between sessions. This appointment format and content are repeated in the subsequent appointments. At the end of treatment, the provider and Veteran will review treatment progress assisted by results of the PCL-5 administered at baseline and during the final appointment. Possible outcomes of this collaborative review are to conclude treatment at four-six appointments or refer the Veteran to specialty MH care for more intensive treatment.

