Provider Training. Drs. [name], [name], and [name] have an established training protocol and will augment this protocol with training case recording ratings to establish competence prior to therapists seeing randomized study patients. [name] as the lead for the PE Therapy Roll Out has extensive experience in fidelity assessment and training to criterion. [name] has been leading the implementation of PE-PC in MTFs in his pilot study and randomized trial. He has years of experience training military providers in this model. Evident within this team is extensive experience working with trauma survivors and expertise in training providers in rapport building within this population as well as manualized therapy components. [name] is the developer of PE and will provide her expertise and input into the design and implementation of training. [name] worked with [name] and [name] on the development of PE-PC protocol. She has been a PE trainer since 2000. Therapists will be trained to a minimal 85% competency on the PE-PC fidelity manual elements prior to seeing randomized cases. While this is a high bar, the brief intervention requires a high level of competence.

Evaluation of PE-PC Fidelity. Treatment fidelity will be assessed by review of a randomly selected 10% of recorded session tapes by a trained fidelity evaluator. In addition, training tapes will be rated for fidelity to ensure therapists are competent prior to their receiving randomized cases. [name] will lead weekly ongoing supervision for PE-PC therapists for the duration of the trial to further ensure consistent therapist competence and fidelity. [name] was trained in PE by [name] and has extensive experience in delivery of and supervision in PE therapy, both in the context of RCTs and routine VA clinical settings.

2. **Control Condition: Treatment as Usual Condition.** Veterans assigned to PCMHI-TAU will receive standard PCMHI care for PTSD in PC that does not include any PTSD-specific therapy in PCMHI but may include referral for specialty care (including specialty MH), medication management or general supportive contact while awaiting referral. All PTSD care received during the study will be

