collected and monitored as TAU. TAU will include the current standard of PTSD care in PCMH (medication, referral to specialty MH, etc.). The type of TAU used will reflect the current practice in PCMH and will not be constrained in the study design. All care will be recorded when a research assistant (RA) conducts a monthly standardized Computerized Patient Record System (CPRS) records review of all MH care received. Each encounter in CPRS will be noted for all randomized patients. Encounter current procedural terminology (CPT) codes, billing codes, duration or contacts will be tracked. No shows and cancellations will also be tracked. Finally, psychoactive medications will be tracked on a monthly basis as well, including medications prescribed, changes, and whether the prescriptions have been filled. While this is most relevant for the TAU condition, these monthly treatment reviews will be conducted on all enrolled Veterans to ensure we can compare rates across groups and note compliance with study requirements.

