Hypothesis 1.1: PE-PC will result in larger increases in function than PCMH-TAU (Week 0 to Week 6) and these differences will be maintained at 12 and 24 weeks post-baseline. Effectiveness will be defined as a group difference at 6 weeks, and maintenance will be defined as whether there is still a group difference at 12 and 24 weeks and whether gains relative to baseline have not been lost. To examine the effectiveness and maintenance of a brief PE-PC protocol compared to PCMH-TAU alone, we will use a unified linear mixed-effects model with WHODAS total scores at 0, 6, 12 and 24 week as the dependent variable. Mixed-effects analyses do not require the assumption of homogeneity of variance in the treatment groups, permits flexible specification of the covariance matrix of the repeated measures and gives unbiased estimate with incomplete data assuming missing at random. The model will include each participant as random intercepts and will adjust for other potentially confounding patient characteristics identified in baseline analysis. Primary predictors will be PE-PC group indicator and time (either as a continuous variable in weeks or as indicators each for 6, 12 and 24 weeks), and interactions of treatment group by appropriate time variable. In this model, time can be modeled in a variety of ways, and a graphical exploration of the cross- sectional means of the outcome by treatment group at each assessment time will guide the decision. For example, if time shows a non-linear effect (e.g., lack of maintenance at 24 weeks), we can model time as categorical indicators for each assessment time and will include interaction terms of PE-PC group indicator by time indicator. Based on the model coefficients and contrasts of the coefficients, outcome at 6 (for effectiveness), 12 and 24 weeks (for maintenance) can be compared separately between groups, and a significant drop in function from 6 to 12 and from 6 to 24 weeks within PE-PC group can be tested for any loss in initial gain (another type of maintenance) if 6 week gain is found to be significant. If no significant loss of initial gain is seen (e.g., no significant difference across the three interaction effects), we will test for the time-averaged PE-PC effect during 6-24 weeks by dropping the interaction terms, and including post randomization time indicator and its interaction with PE-PC group indicator where the coefficient of the interaction term will be interpreted as the time-averaged PE-PC effect during period 6 to 24. Although not our main hypothesis, within each treatment group, improvement from baseline in outcome at each follow-up will also be determined based on the model. Residuals will be examined for ceiling or floor effects, and if ceiling or floor effect is evident, we will consider reanalyzing function using the dichotomized WHODAS total score (using hierarchical logistic regression model and recognizing that our study will likely not have adequate statistical power for H1 based on the dichotomized response), and will also repeat the primary analysis using the overall impairment score of the B-IPF.

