
The study will have both drop-outs and lost to follow-up. We will prepare a consort flow diagram to describe disposition of Veterans at each stage of the research. We expect about 10% loss at 6 weeks. This estimate may seem low but the period of follow-up is short and patients will be followed regardless of treatment completion to fully model response. Primary analytic cohort will be intent-to-treat. Every effort, including follow-up phone calls, will be made to collect follow-up data to reduce missingness to a minimum. We will also collect the reason for missing data such as "patient refusal" or "scheduling complication" to have a better understanding of the mechanisms of missingness. We will check for pattern of missingness, compare rate of missingness at each follow-up time and dropouts between

groups, and compare reasons for dropout between groups. We will also check if dropout depends on covariates and will include those covariates in the models described above; the analysis using linear mixed-effects model will give us an unbiased estimate assuming missing at random. When data are missing for items within scales, we will use recommended imputation procedures.

Hypothesis 2.1-2: PE-PC will result in larger reductions in PTSD severity (H2.1: CAPS and PCL-5 (49, 50)) and depression severity (H2.2) than PCMHI-TAU (Week 0 to Week 6), and these differences will be maintained at 12 weeks and 24 weeks post-baseline, larger reductions in depression than PCMHI-TAU (Week 0 to Week 6) and these differences will be maintained at 12 weeks and 24 weeks post-baseline. We will use a similar analytic approach as for Aim 1 using a linear mixed-effects regression model for each outcome measure with both baseline and all follow-up assessment data as the dependent variable. The model will include PE-PC group indicator, follow-up time indicators, and interactions of treatment group by follow-up time indicators. Statistically significant interaction terms with negative parameter estimates will provide evidence for significantly greater symptom reduction at each follow-up time in those randomized to PE-PC compared with PCMHI-TAU group. Similar to the analytic approach described for Aim 1, maintenance will also be assessed as drop at 24 weeks in improvement gained at 6 weeks, and this will be assessed for both PTSD and depression symptoms using appropriate contrasts based on the coefficients from the linear mixed-effects model.

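### Entry to the intent-to-treat set depends on attending a first session after randomization, and usual care has no such session, so the primary set is not intent-to-treat as written

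*Combined protocol and SAP*

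**What the plan says.** - **Definition of the set.** Section 9, Randomization Procedures: "Once a patient is randomized and attends the first session, he or she will be entered into the study and included in the intent-to-treat" (the sentence goes on to name the planned analysis). No other passage defines the set.
- **Use of the set.** Section 10, Data Analytic Plan: "Primary analytic cohort will be intent-to-treat". The term is not redefined there, so the section 9 rule governs the primary week-6 WHODAS comparison.
- **PE-PC arm.** Section 3, Treatment Conditions, schedules four to six appointments and describes the opening one: "At the first 30-minute appointment, the PCMHI provider will review the" workbook. The first session can therefore be identified, although the plan never formally ties the section 9 term to it.
- **TAU arm.** Section 3, Control Condition, says that care "may include referral for specialty care (including specialty MH), medication management or general supportive contact while awaiting referral". It adds: "The type of TAU used will reflect the current practice in PCMH and will not be constrained in the study design". No session schedule is given.
- **Data already planned.** Section 3: "Each encounter in CPRS will be noted for all randomized patients", and "All Veterans will complete a baseline assessment (week 0) prior to randomization". Section 10, Hypothesis 1.1: "we will use a unified linear mixed-effects model with WHODAS total scores at 0, 6, 12 and 24 week as the dependent variable".

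**The concern.** An intent-to-treat set is fixed by randomization alone. Here entry needs a second event, attendance, that occurs after allocation and can depend on the arm: a patient may decline exposure work but accept a medication review, or the reverse. Comparing attenders with attenders, or PE-PC attenders with everyone in TAU, gives up the balance that randomization provides.

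There is a practical problem as well. The analyst cannot build the TAU set from the plan. Someone must later decide whether a referral, a prescription or a supportive call counts as a first session. The research assistant who reviews the records for encounters (section 3) is among the staff who know the allocation (section 9).

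Read literally, a non-attender is also not entered into the study. That leaves it unclear whether the week 6, 12 and 24 assessments apply to that patient. Outcomes not collected at week 6 cannot be recovered later.

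**Working it through.** **1. The rule applied to each arm**

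| Reading | PE-PC | TAU | Result |
|---|---|---|---|
| A | Non-attenders of the described first appointment removed | Nobody removed | Selection in one arm only |
| B | As in A | Patients removed by some unwritten test of first contact | Selection in both arms, on different events |

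Neither reading gives all randomized patients in the arm assigned.

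**2. The plan's power figure**

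Inputs from Power Analysis (section 10): 60 per arm, 10% loss at week 6, effect 0.54 SD, two-sided alpha 0.05.

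- Evaluable per arm: 60 × 0.90 = 54.
- SE = √(1/54 + 1/54) = 0.1925, and 0.54 / 0.1925 = 2.806.
- Power is 80.1% by the normal approximation and 79.4% by noncentral t. The stated 80% reproduces.

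**3. Bias under reading A**

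The documents give neither input, so both are assumptions:

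- *p*, the share of one arm excluded: 5% to 15%. For scale, section 6 estimates 15% attrition during treatment, and section 2 reports 12% drop from PE-PC in the earlier military trial. Neither is stated to be a never-started rate.
- *g*, the difference in mean outcome between attenders and non-attenders: 0.25 to 0.8 SD.

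Bias = *p* × *g*. With *n* evaluable per arm before exclusion, SE = √(1/(*n*(1−*p*)) + 1/*n*). Type I error is the two-sided rejection rate of a t-test with noncentrality bias/SE.

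| *p* | Bias, *g* = 0.25 to 0.8 (SD) | Share of 0.54 | Type I error, *n* = 54 |
|---|---|---|---|
| 5% | 0.0125 to 0.040 | 2% to 7% | 0.051 to 0.055 |
| 10% | 0.025 to 0.080 | 5% to 15% | 0.052 to 0.069 |
| 15% | 0.0375 to 0.120 | 7% to 22% | 0.054 to 0.091 |

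Worked case, *p* = 15%, *g* = 0.8: bias = 0.15 × 0.8 = 0.12. The arms are 54 × 0.85 = 45.9 and 54, SE = 0.2008, noncentrality = 0.598, type I error = 0.091.

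Section 6 implies a larger trial, with 187 left after screen failures. If 187 are randomized and 10% are lost, the evaluable number is 93.5 × 0.90 = 84.15 per arm. At *p* = 15% type I error is then 0.056 to 0.115.

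A simulation of 40,000 null trials (54 per arm, *p* = 15%) gave bias 0.039 and 0.120 SD at the two ends of *g*, with type I error 0.053 and 0.089. With equal exclusion and an equal gap in both arms, bias was 0.000 and type I error 0.049.

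**4. Can the planned model use everyone?**

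Yes. Baseline WHODAS is collected before randomization and is part of the dependent variable, so each randomized patient should contribute at least one value.

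**The case against.** **The wording may only be loose.** Section 10 names intent-to-treat without any condition, section 9 calls patients enrolled before they are randomized, and section 3 tracks everyone randomized. The sponsor may well intend the full set. That is possible, but the only sentence that defines the set says otherwise, and a plan has to be executable as written.

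**Follow-up appears to cover everyone.** Sections 1, 3 and 4 say that all Veterans complete the assessments. Section 9 ties follow-up payments to randomization, not attendance. Section 10 follows patients who do not complete treatment, and section 11 promises contact whether or not they finish the trial. Taken together, these point towards follow-up of all randomized patients, and that weakens the doubt about data collection. None names patients who never start, and none returns them to the analysis set.

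**The numbers are assumptions.** This stands. Neither *p* nor *g* has a source in the documents, and at 5% to 10% excluded the inflation is small over most of the range. The calculation is a two-sample comparison at week 6, whereas the plan uses a mixed model with repeated measures, so the exact figures would differ. The 84-per-arm case is a scenario that no section states: it leaves out section 6's 15% treatment attrition because patients are to be followed whether or not they complete treatment.

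**The mixed model handles missing data.** Only for patients who are in the dataset. It cannot recover those removed by the set definition.

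**Conclusion.** The concern holds. The stated rule makes the primary set depend on a post-randomization event, and that event has no counterpart in TAU. This rests on the text and not on any calculation.

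The size and direction of the bias are unknown. If only PE-PC loses non-attenders and they would have done worse, the bias favours PE-PC; if they would have done better, it runs the other way. Over the assumed range it is 0.01 to 0.12 SD, up to 22% of the target effect, with type I error of 0.051 to 0.091 at 54 per arm. It is nil if exclusions and gaps match across arms. No loss of power is claimed, because section 6 and Power Analysis disagree on whether 120 is the number completing or the number enrolled.

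The change should be made before any analysis. A CONSORT diagram and no-show tracking would show the selection but not remove it.

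**What to change.** Replace the section 9 sentence with:

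> *All randomized patients are in the intent-to-treat set in the arm assigned, whether or not they attend any session, and are invited to the week 6, 12 and 24 assessments unless they withdraw consent.*

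Also:

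- Keep attendance at one or more sessions as a sensitivity set only, with a written TAU equivalent.
- Report first-session non-attendance by arm in the CONSORT diagram.
- State that assessment contacts extend to patients who never start.

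**Cost.** The change takes one sentence and one CONSORT line. Encounters and no-shows are already tracked for all randomized patients. If 15% of one arm never starts, that is 60 × 0.15 = 9 patients, or 93.5 × 0.15 ≈ 14 in the larger trial. At three $50 payments each, the outlay is at most $1,350 to $2,100 plus staff time, and section 9's payment terms may already cover it.

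**Downside.** The planned sample size is unchanged, and power stays at about 80% if 0.54 is already the effect among all randomized. If 0.54 holds only for attenders, and 15% of PE-PC patients never start and gain nothing, the effect becomes 0.54 × 0.85 = 0.459. By noncentral t, power then falls from 79% to about 66% at 54 per arm, and would be 84% at 84 per arm. The documents do not say which applies. The diluted figure would be the effect of assignment, which is what an intent-to-treat analysis estimates.
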